3. OBJECTIVES

3.1. Primary Objective(s)

Immunogenicity objective:

1. To demonstrate a sufficient immune response following a booster dose of MenACWY-CRM (Menveo) vaccine, given to subjects who previously received Menveo, as measured by the percentage of subjects with hSBA seroresponse¹ against *N. meningitidis* serogroups A, C, W and Y at Day 29 after vaccination
2. To demonstrate a sufficient immune response following a booster dose of MenACWY-CRM (Menveo) vaccine, given to subjects who previously received Menactra, as measured by the percentage of subjects with hSBA seroresponse¹ against *N. meningitidis* serogroups A, C, W and Y at Day 29 after vaccination

Criteria to demonstrate immune response sufficiency: The immune response sufficiency will be tested sequentially; first in the group of subjects who received primary vaccination with Menveo and, if met, also in the group of subjects who received primary vaccination with Menactra. The immune response will be considered as sufficient if the lower limit of the one-sided 97.5% CI for percentage of subjects with hSBA seroresponse¹ against serogroups A, C, W and Y is greater than 75%. The study will be considered successful if the immune response sufficiency will be demonstrated at least in the group of subjects who received primary vaccination with Menveo.

3.2. Secondary Objective(s)

[figure not shown]
Secondary Immunogenicity objectives:

1. To compare the immune responses over time following a booster dose of MenACWY-CRM vaccine, between subjects who previously received Menveo,

¹ Seroresponse is defined for this booster study as follows: For subjects with pre-vaccination titers <4, post-vaccination titers ≥ 16 ; for subjects with pre-vaccination titers ≥ 4 , post vaccination titers at least 4 times the pre-vaccination titers.

Statistical Analysis Plan

| | | |
|--|------------|------------------|
| Study alias & e-track number(s): V59 77 (205352) | Version: 1 | Date: 19-09-2016 |
|--|------------|------------------|

 GSK GlaxoSmithKline

subjects who previously received Menactra, and subjects who previously received Menveo or Menactra (pooled vaccine group) and following a single dose in vaccine-naïve individuals, as measured by the percentages of subjects with hSBA seroresponse¹, hSBA titers ≥ 8 and ≥ 16 , and hSBA GMTs against *N. meningitidis* serogroups A, C, W and Y at Day 1, Day 4, Day 6, and Day 29 after vaccination.

2. To assess persistence of bactericidal antibodies against serogroups A, C, W and Y at approximately 4-6 years after the primary vaccination with Menveo and after the primary vaccination with Menactra in comparison with naturally-acquired level in vaccine-naïve individuals, as measured by the percentages of subjects with hSBA titers ≥ 8 and hSBA GMTs at Day 1.

Secondary Safety objectives:

To assess the reactogenicity and safety of MenACWY-CRM vaccine when administered to subjects who previously received Menveo or Menactra and vaccine-naïve individuals.

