4. SELECTION OF STUDY POPULATION

4.1 Inclusion Criteria

In order to participate in this study, all subjects must meet ALL of the inclusion criteria described.

1. Individuals of 18 through 55 years of age on the day of informed consent or assent.
2. Individuals who received Menveo 4 to 6 years prior to enrolment at an age of 11 years or older (Menveo-Menveo group)

OR

Individuals who received Menactra 4 to 6 years prior to enrolment at an age of 11 years or older (Menactra-Menveo group)

OR

Individuals who have not received any previous meningococcal vaccine (Naive group).

3. Individuals who have voluntarily given written informed consent (and/or assent, if applicable) after the nature of the study has been explained according to local regulatory requirements, prior to study entry. If the subject is under age 18 at the time of enrolment, the parent(s)/legal guardian(s) of the subject should have voluntarily given written informed consent.
4. Individuals who can comply with study procedures including follow-up¹.

S. Males

Or

Females of non-childbearing potential²

Or

¹ A subject and/or parent(s)/legal guardian(s) is/are considered to be compliant if the Investigator judges that the subject will complete the Subject Diary and return for all the follow-up visits scheduled in the study.

² A female is considered to be of non-childbearing potential prior to menarche and after natural or induced menopause. Natural menopause is recognized to have occurred after 12 consecutive months of amenorrhea for which there is no other obvious pathological or physiological cause. Induced menopause is recognized to have occurred after hysterectomy, after bilateral oophorectomy, or iatrogenic ablation of ovarian function.

Females of childbearing potential who are using an effective birth control method¹ which they intend to use for at least 30 days after the study vaccination

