5.1.2 Screening

Subject identification numbers will be assigned sequentially to the subjects who have consented to participate in the study, according to the range of subject identification numbers allocated to each study center. The eligibility of the subject will be determined based on the inclusion and exclusion criteria listed in [section 4, Selection of Study Population](#) and evaluated during this screening procedure.

Prior to study enrolment, demographic data will be collected from the subject, including: date of birth, gender, race, ethnicity, prior vaccination against meningitis. Note: Appropriate written documentation of the brand of primary vaccination (Menveo or Menactra) and vaccination date must be provided prior to enrollment.

Medical history will also be collected, including but not limited to any medical history that may be relevant to subject eligibility for study participation such as prior vaccinations, concomitant medications, and previous and ongoing illnesses or injuries. Relevant medical history can also include any medical history that contributes to the understanding of an adverse event that occurs during study participation, if it represents an exacerbation of an underlying disease/pre-existing problem.

Review of systems is a structured interview that queries the subject and/or parent(s)/legal guardian(s) as to any complaints the subject has experienced across each organ system. This will be performed before enrolment and used to guide physical examination.

If applicable, prior and concomitant medications or vaccinations taken prior to start of study should be collected (refer to [section 6.5, Prior and Concomitant Medications and Vaccines](#) for further details).

Collect vital signs (heartrate, blood pressure, and temperature (preferably taken orally). Measure height and weight.

Perform pregnancy testing in women of childbearing potential (refer to [section 3.5, Collection of Clinical Specimens](#) for additional information)

A general physical examination is to be performed by a qualified health care practitioner. "Qualified health care practitioner" refers to any licensed health care professional who is permitted by institutional policy to perform physical examinations and who is identified within the Study Staff Signature Log.

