6.1. Demography

6.1.1. Analysis of demographics/baseline characteristics planned in the protocol

Descriptive statistics (mean, standard deviation, median, minimum and maximum) for age, height and weight at enrolment will be calculated overall and by study group.

| | |
|--|---|
| Statistical Analysis Plan |  GlaxoSmithKline |
| Study alias & e-track number(s): V59 77 (205352) | |
| Version: 1 | Date: 19-09-2016 |

Distributions of subjects by sex, race and ethnic origin will be summarized overall and by study group.

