For each study group and in the pooled group (Menveo-Menveo and Menactra-Menveo), the percentage of subjects with hSBA titer ≥ 8 and ≥ 16 and associated two-sided 95% Clopper-Pearson CIs will be computed by the *N. meningitidis* serogroups A, C, W and Y test strains on Day 1, Day 4, Day 6 and Day 29 (as applicable, depending on blood draw schedule).

Differences in percentages and associated 95% CIs between study groups will be calculated using the Miettinen & Nurminen score method.

| Statistical Analysis Plan | |  GSK GlaxoSmithKline |
|--|------------------|---|
| Study alias & e-track number(s): V59 77 (205352) | Version: 1 | |
| | Date: 19-09-2016 | |

In a descriptive fashion - using the difference in percentages and 95% CIs - the previously vaccinated groups (individually and pooled [Menveo-Menveo and Menactra-Menveo]) will be compared to the naïve group. Also the two previously vaccinated groups will be compared to each other.

As sensitivity analyses, the difference in percentages will also be obtained from a log-linear model adjusting for pre-vaccination titer.

Between-group Ratios of GMTs (Adjusted and Unadjusted)

The between-group ratio of hSBA GMTs and corresponding 95% CI, at each of Visit Day 1 (Persistence), Day 4, Day 6 and Day 29 against each *N. meningitidis* serogroups A, C, W and Y test strains will be obtained by exponentiating the mean between-group differences in log-transformed titers and the corresponding 95% CIs at each of the timepoints specified.

Additionally, adjusted ratio of GMTs will be obtained from ANCOVA models including pre-vaccination titer as factors in the model.

The previously vaccinated groups (individually and pooled [Menveo-Menveo and Menactra-Menveo]) will be compared to the naïve group at each timepoint – descriptively – using the ratios of GMTs.

The two previously vaccinated groups will be compared at each timepoint using GMT ratios.

Within-group GMRs (Adjusted and Unadjusted)

Within each study group and for each serogroup, GMRs will be calculated, as applicable, at:

- Visit Day 4 versus at Visit Day 1;
- Visit Day 6 versus at Visit Day 1; and
- Visit Day 29 versus at Visit Day 1.

The unadjusted GMRs and 95% CIs will be constructed by exponentiating the mean within-group differences in log-transformed titers and the corresponding 95% CIs.

| | |
|--|------------------|
| Statistical Analysis Plan | |
| Study alias & e-track number(s): V59 77 (205352) | |
| Version: 1 | Date: 19-09-2016 |

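### The Day 1 comparison of Menveo-primed with Menactra-primed subjects ignores time since priming, and the one planned covariate cannot adjust it

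*SAP*

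**What the plan says.** The persistence objective in SAP 3.2 is "To assess persistence of bactericidal antibodies against serogroups A, C, W and Y at approximately 4-6 years after the primary vaccination with Menveo", and the same after Menactra. Its comparator is the naturally acquired level in naive subjects. The contrast between brands comes from elsewhere: the first secondary immunogenicity objective in SAP 3.2, the between-group endpoints in SAP 4.2, and the methods in SAP 6.3.1.

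- **GMTs.** Between-group ratios are planned "at each of Visit Day 1 (Persistence), Day 4, Day 6 and Day 29", and "The two previously vaccinated groups will be compared at each timepoint using GMT ratios".
- **Percentages.** For titers ≥8 and ≥16, with Day 1 among the listed days: "Also the two previously vaccinated groups will be compared to each other".
- **Adjustment.** SAP 6.3.1 says adjusted estimates are there to deal with possible baseline imbalance between groups. The ANCOVA for GMT ratios and the log-linear sensitivity model for percentages each name one covariate, pre-vaccination titer.
- **Baseline tables.** SAP 6.1.1 gives descriptive statistics "for age, height and weight at enrolment will be calculated overall and by study group", plus sex, race and ethnic origin. SAP 6.1.2 adds medical history.
- **Subgroups.** SAP 6.3.2 names sex and race, for the primary objectives only.
- **The interval.** Protocol 4.1 admits subjects primed 4 to 6 years earlier, with the same rule for both brands. Protocol 5.1.2 states: "Appropriate written documentation of the brand of primary vaccination (Menveo or Menactra) and vaccination date must be provided prior to enrollment".

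**The concern.** Only the blood-draw schedule is randomised (SAP 2; Protocol 5.1.4.2). Which vaccine a subject was primed with, and when, is past history, so nothing in the design balances time since priming between the two primed groups. If antibody wanes over these years, a group primed longer ago will tend to have lower Day 1 titers whatever the brand.

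The interval can be worked out for each primed subject from a date that must be documented, but the SAP text puts it in no table, subgroup or model. At stake is how the Day 1 brand contrast is read: a reader given only the crude ratio and differences has no means of judging how much is elapsed time.

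**Working it through.** **1. Can the planned adjustment work at Day 1?** The Day 1 sample is drawn before vaccination, so the Day 1 titer is the pre-vaccination titer. In the ANCOVA at Day 1, outcome and covariate would be the same variable. In the log-linear model for titer ≥8 or ≥16 at Day 1, the outcome would be a cut-off applied to the covariate. Neither gives a usable adjusted brand contrast, so the stated aim of handling baseline imbalance cannot be met at this timepoint. At Days 4, 6 and 29 the covariate is a genuine baseline value.

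**2. The plan's own figures.** The documents give no sample size, power or precision for the Day 1 contrast. The evaluable number reproduces: 300 × (1 − 0.10) = 270 per primed group. So does the primary-objective power in Protocol 8.5: 0.99^4 = 0.961 against the stated 0.96. Nothing here alters either.

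**3. Size of a shift due to elapsed time alone.** With no brand effect and a constant annual loss w, a difference d in mean interval (years) gives a Day 1 GMT ratio of (1 − w)^d. Both w and d are assumptions; the documents give only the 4-to-6-year limits.

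| Annual loss w | d = 0.5 | d = 1 |
|---|---|---|
| 15% | 0.85^0.5 = 0.92 | 0.85 |
| 30% | 0.70^0.5 = 0.84 | 0.70 |

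A 0.25-year difference at 10-30% loss gives 0.97 to 0.92.

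**4. Against sampling error.** The 95% CI factor for a GMT ratio at 270 per group is 10^(1.96 × SD × √(2/270)), with an assumed SD of log10 titer:

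- SD 0.5: 1.21, or about 0.82 to 1.21 around a ratio of 1.
- SD 0.7: 1.31, or about 0.76 to 1.31.
- SD 0.9: 1.42, or about 0.70 to 1.42.

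The 0.92 to 0.84 shift lies inside all three. It would move the estimate but not by itself make the interval exclude 1.

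**5. Precision cost of adjusting.** Take a within-group interval SD of 0.58 years (an even spread over two years: 2/√12). The variance inflation is 1 + d²/(4 × 0.58²), which is about 1.05 at d = 0.25 and 1.19 at d = 0.5. The latter widens the standard error by about 9% (√1.19 = 1.09).

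**The case against.** A good deal can be said for the plan.

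- **The persistence objective is against naive subjects.** They have no interval since priming, so an imbalance between brands cannot bias that comparison. A reader might infer that the persistence objective itself is compromised; the documents do not support that. This stands.
- **The brand contrast carries little inferential weight.** Protocol 8.4.3.3.1 makes secondary immunogenicity descriptive without formal tests, and SAP 7 confines such comparisons to supportive or hypothesis-generating use. This stands, and limits the seriousness. It does not make the crude contrast the better description.
- **No imbalance is shown.** Both groups share the same limits. A 1-year mean difference with even spread would need one brand wholly at 4-5 years and the other wholly at 5-6. The larger figures above are therefore extreme cases. Also, SAP 11.2 sets values below the quantification limit to half that limit; if many Day 1 titers sit there, a constant percentage loss overstates the ratio. Both points stand.
- **Four versus six years is not the trial's question.** The background asks about a booster at about 5 years, and there are no exploratory objectives. Splitting persistence at 5 years would be an extra, not a repair.
- **An interval table may exist.** SAP 8.1 and 10 refer to a separate output list that is not in the documents. Protocol 5.1.2 also counts prior meningitis vaccination among demographic data, which SAP 6.1.2 tabulates. Neither promises an interval summary, but the point is confined to the SAP text.

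**Conclusion.** The point holds for the Day 1 Menveo-versus-Menactra contrast. Brand is not randomised, the interval may span two years, the SAP text does not use it, and the only covariate is the Day 1 outcome itself. Any bias depends on intervals differing by brand, which the documents neither show nor exclude. Its size is illustrative: a GMT ratio of 0.92 to 0.84 for a 0.5-year difference in mean interval, resting on an assumed constant loss of 15-30% a year.

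A reader might go further and infer that waning time and brand cannot be separated in this trial. That is true of the outputs planned in the SAP text but not of the data, because the priming dates must be documented before enrolment. The primary objective, its significance level and its sample size are untouched. This is a worthwhile, nearly free improvement to a descriptive analysis, not a threat to the trial's main conclusion.

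**What to change.** - **SAP 6.1.2:** summarise time since primary vaccination by primed group (mean, SD, median, range).
- **SAP 6.3.2:** for the Day 1 Menveo-Menactra GMT ratio and the differences in percentage with titer ≥8 and ≥16, report estimates adjusted for, or stratified by, time since priming beside the crude ones. State that pre-vaccination titer is not used as a covariate at Day 1, and that interval adjustment does not remove other confounding, such as age at priming.
- **Optional:** Day 1 persistence tables by interval (4 to <5 and 5 to 6 years) within each primed group.

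The cost is a few lines of SAP text and a small number of tables. No visit, sample, significance level or sample size changes. The sponsor should confirm that the priming date is held in the study database: Protocol 5.1.2 requires it to be documented but does not expressly call it an eCRF field.

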4. ENDPOINTS

4.1. Primary Endpoints

Primary Immunogenicity Endpoint

The following measure will be summarized for the Menveo-Menveo and Menactra-Menveo groups:

1. Percentage of subjects with hSBA seroresponse² against *N. meningitidis* serogroups A, C, W and Y at Day 29.

² Seroresponse is defined for this booster study as follows: For subjects with pre-vaccination titers <4, post-vaccination titers ≥ 16 ; for subjects with pre-vaccination titers ≥ 4 , post vaccination titers at least 4 times the pre-vaccination titers.

Statistical Analysis Plan

| | | |
|--|------------|------------------|
| Study alias & e-track number(s): V59 77 (205352) | Version: 1 | Date: 19-09-2016 |
|--|------------|------------------|

 GSK GlaxoSmithKline

4.2. Secondary Endpoints

Secondary Safety Endpoints

Safety of the study vaccine will be assessed in the Menveo-Menveo, Menactra-Menveo, Naive and the pooled (Menveo-Menveo and Menactra-Menveo) groups in terms of the frequencies (percentages) of reported adverse events including:

1. Any unsolicited AEs reported within 30 minutes after vaccination;
2. Solicited local and systemic AEs reported from Day 1 (6 hours) through Day 7 after vaccination;
3. Other indicators of reactogenicity (e.g. use of analgesics / antipyretics, body temperature) within 7 days after vaccination;
4. All unsolicited AEs reported from Day 1 through Day 29 after vaccination;
5. Medically-attended AEs, AEs leading to withdrawal and SAEs reported from Day 1 through Day 181 (entire study period).

Adverse events will be coded using MedDRA preferred terms as applicable.

[figure not shown]
Secondary Immunogenicity Endpoints

The following measures will be summarized for Menveo-Menveo, Menactra-Menveo, Naive and the pooled (Menveo-Menveo and Menactra-Menveo) groups:

1. Percentage of subjects with hSBA titer ≥ 8 and ≥ 16 against *N. meningitidis* serogroups A, C, W and Y at Day 1, Day 4, Day 6 and Day 29 and between-group differences;
2. Percentages of subjects with hSBA seroresponse³ against *N. meningitidis* serogroups A, C, W and Y at Day 4, Day 6 and Day 29 and between-group differences;

³ Seroresponse is defined for this booster study as follows: For subjects with pre-vaccination titers <4, post-vaccination titers ≥ 16 ; for subjects with pre-vaccination titers ≥ 4 , post vaccination titers at least 4 times the pre-vaccination titers.

Statistical Analysis Plan

| | |
|--|--|
| Study alias & e-track number(s): V59 77 (205352) |  GSK |
| Version: 1 | Date: 19-09-2016 |

3. hSBA GMTs against *N. meningitidis* serogroup A, C, W and Y at Day 1, Day 4, Day 6 and Day 29;
4. Ratios of hSBA GMTs at Day 1, Day 4, Day 6 and Day 29 (between study groups).
5. hSBA Geometric Mean Ratios (GMRs) at Day 4, Day 6, and Day 29 compared to Day 1 (within study groups).

5. ANALYSIS SETS

5.1. Definition

5.1.1. All Enrolled Set

All screened subjects who provide informed consent and provide demographic and/or baseline screening assessments, regardless of the subject's randomization and treatment status in the study, and received a Subject ID.

5.1.2. All Exposed Set

All subjects in the enrolled set who receive a study vaccination.

5.1.3. Safety Sets

Solicited Safety Set (solicited local and systemic adverse events and other solicited adverse events)

All subjects in the Exposed Set with any solicited adverse event data.

Unsolicited Safety Set (unsolicited adverse events)

All subjects in the Exposed Set with unsolicited adverse event data.

Overall Safety Set

All subjects who are in the Solicited Safety Set and/or Unsolicited Safety Set.

Statistical Analysis Plan

| | |
|--|--|
| Study alias & e-track number(s): V59 77 (205352) |  GSK |
| Version: 1 | Date: 19-09-2016 |

5.1.4. Immunogenicity Sets

Full Analysis Set (FAS)

FAS (Day 1)

All subjects in the All Enrolled Set who:

- are randomized;
- provide evaluable serum samples at Day 1 whose result is available for at least one serogroup.

FAS (Day 29)

All subjects in the All Enrolled Set who:

- are randomized;
- receive the study vaccination;
- provide evaluable serum samples at Day 1 whose result is available for at least one serogroup (this condition is not required for the analyses on hSBA titer ≥ 8 and ≥ 16 , GMTs and GMRs calculated at specific timepoints);
- provide evaluable serum samples at Day 29 whose result is available for at least one serogroup.

Per Protocol (PP) Set

A PPS will be defined for each FAS described in the previous Section with additional criteria specified below.

All subjects in the FAS Immunogenicity who:

- Have no protocol deviations leading to exclusion (see section 5.2.3) as defined prior to unblinding / analysis.
- Are not excluded due to other reasons defined prior to the analysis (see section 5.2.3)

Examples for subjects excluded due to other reasons than protocol deviations are:

- Subjects who withdrew informed consent.

| | |
|--|------------------|
| Statistical Analysis Plan | |
| Study alias & e-track number(s): V59 77 (205352) | |
| Version: 1 | Date: 19-09-2016 |

5.2. Criteria for eliminating data from Analysis Sets

Elimination codes are used to identify subjects to be eliminated from analysis. Detail is provided below for each sets. A consolidated table is also available in Annex 2.

5.2.1. Elimination from Exposed Set (ES)

Code 100 (Study vaccine not administered at all) will be used for identifying subjects eliminated from ES.

5.2.2. Elimination from Full Analysis Set (FAS)

Code 110.x (Serological results not available at Day x) will be used for identifying subjects eliminated from FAS Day x.

5.2.3. Elimination from Per-protocol analysis Set (PPS)

5.2.3.1. Excluded subjects

A subject will be excluded from the PPS analysis under the following conditions:

| Code | Condition under which the code is used |
|------|--|
| 120 | Randomization failure |
| 140 | Vaccination not according to protocol |
| 150 | Administration of forbidden vaccine |
| 200 | Subject did not meet entry criteria |
| 230 | Administration of forbidden medication |
| 240 | Underlying medical condition forbidden by the protocol |
| 250 | Concomitant infection related to the vaccine which may influence immune response |

| | |
|--|------------------------|
| Statistical Analysis Plan | |
| Study alias & e-track number(s): V59 77 (205352) | gsk GlaxoSmithKline |
| Version: 1 Date: 19-09-2016 | |

| | |
|-----|--|
| 260 | Did not comply with study vaccination schedule |
|-----|--|

